#### **6.4.3.5 Scoring of WHO Clinical Outcome Scale (9-point Scale)**

The number and percentage of patients for each WHO clinical outcome score will be summarized.

The combined two highest treatment groups will be compared to placebo in addition to the comparison of individual doses at the following visits (Baseline, Day3, Day5, Day10, Day14 and Day 28/EOS) using the Mann-Whitney-Wilcoxon test. Since Day 1 corresponds to the date of first dose, Day 1 will be used for baseline. A frequency distribution plot of WHO clinical outcome scale at each study visit on the ITT population will also be presented (Section 7, Figure 9).

A listing of the WHO clinical outcome scale score at each time point will be provided (Section 7, Listing 8).

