## 2. OBJECTIVES AND ENDPOINTS

### 2.1. Objectives

The primary efficacy objective of the study is:

- To evaluate the time to sustained clinical resolution of symptoms in patients with confirmed, mild to moderate, symptomatic COVID-19 treated with dalcetrapib.

Sustained clinical resolution is defined as occurring when no key COVID-19 related symptom has a score higher than 1 over a 72-hour period (as documented using an electronic patient-reported outcome [ePRO] instrument), except for sense of smell and taste (items 13 and 14) where the score should be 0 over a 72-hour period. The time to resolution will be taken as the time from randomization until the first day of the last 72-hour period where the patient meets the definition of resolution within 28 days. Patients who do not meet the definition of resolution 28 days after randomization will be considered not resolved.

The secondary efficacy objectives of the study are:

- To evaluate the change from baseline in COVID-19 symptom severity score at all collected time points
- To evaluate time to complete clinical resolution, defined in the same way as the primary endpoint, but considering that all symptoms must resolve to a score of 0 for 72 hours
- To evaluate the time to viral clearance using SARS-CoV-2 polymerase chain reaction (PCR)
- To evaluate change from baseline in log10 viral load
- To evaluate the WHO Clinical Outcome Scale (9-point scale) at Day 3, Day 5, Day 10, and Day 28
- Rate of hospitalization through Day 28
- To evaluate the rate of progression to oxygen therapy through Day 28
- To evaluate the duration of hospitalization
- To evaluate the mortality rate by Day 28

The safety objective of the study is:

- To assess the safety and tolerability of dalcetrapib active doses compared to placebo in patients with COVID-19

The pharmacokinetics (PK) objective of the study is:

- To evaluate the PK of dalcetrapib in patients with COVID-19

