#### ***8.4.2.3. Scoring of WHO Clinical Outcome Scale (9-point Scale)***

The number and percentage of patients for each WHO clinical outcome score will be summarized. An ordinal logistic regression analysis for the specified time points will be presented as odds ratio, with associated 95% CI and p-value.

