## 2 STUDY DESCRIPTION

### 2.1 Study Design

This is a randomized, double-blind, multicenter Phase 2a proof-of-concept study in outpatients with confirmed, mild to moderate, symptomatic COVID-19. Electronic informed consent must be obtained from all patients or their legally authorized representative during screening before any study-related procedures are performed. The Screening/Baseline assessments may be performed at the study site or as a home visit.

A total of 208 patients will be randomized to receive 900, 1800, or 3600 mg of dalcetrapib or placebo once daily (52 patients to each of 900 mg, 1800 mg, 3600 mg and placebo) for 10 days. Patients will be randomized and receive first dose of study drug within 72 hours of receiving a positive PCR or Point-of-care test for SARS-CoV-2. Patients need to have at least two of the 14 common COVID-19-related symptoms described in the inclusion criteria rated as mild or moderate, as evaluated by ePRO assessment or eCRF. Symptoms will be assessed at each study visit daily for the first 10 days, then at Day 14 and Day 28, and as clinically indicated. Symptoms will be evaluated as absent, mild, moderate, or severe depending on their impact on activities of daily living. SARS-CoV-2 viral loads will be obtained by both saliva (Oragene) collection and mid-turbinate nasal swab self-collection under supervision of a healthcare professional (virtual or home visit) at Screening/Baseline, Day 1, Day 3, Day 5, Day 7, Day 10, and Day 28. Patients who require hospitalization after initiation of study treatment will be followed for safety assessment through Day 28.

The study will be overseen by an independent Data Monitoring Committee (DMC). The DMC will review the safety data throughout the study. The DMC and Sponsor will review efficacy data at the interim analysis and at the end of the study. A DMC Charter, which includes detailed processes, will be prepared. One interim analysis will be conducted once 120 patients have a follow-up time of 28 days.

All patients will be closely monitored for adverse events (AEs) from informed consent for at least 18 days after the final dose of study treatment (until Day 28±2). Patients who withdraw early from the

study treatment will have follow-up phone calls to collect safety data until End of Study on Day 28±2. On days of laboratory assessments and PK sample collection, outpatient subjects may have a home visit.

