#### 6.2 Statistical Considerations

Continuous variables will be summarized by the standard descriptive statistics: number of patients (n), mean, standard deviation, median, Q1, Q3, minimum, and maximum, along with confidence interval (CI) for outcome measures when appropriate. Frequency of patient or events and percentages will be summarized for categorical variables, again with CI when appropriate. Time to event variables will be summarized using Kaplan-Meier methods.

All statistical tests will be conducted at a two-sided 0.20 significance level.

Statistical analyses will be performed using SAS Version 9.4 or higher.

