### 6.2.3 Multiplicity/Multiple Testing

The primary analysis compares the combined two highest dalcetrapib dose groups against placebo as well as each treatment group individually. No adjustments will be made for multiple testing.

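### The SAP tests the WHO scale between arms at Baseline, where any difference can only be chance, and does not use the baseline score in the later tests, where it might help

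*SAP*

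**What the plan says.** SAP 6.4.3.5 sets out the WHO-scale analysis. The contrasts are: "The combined two highest treatment groups will be compared to placebo in addition to the comparison of individual doses". They are made "at the following visits (Baseline, Day3, Day5, Day10, Day14 and Day 28/EOS) using the Mann-Whitney-Wilcoxon test". The same section fixes which assessment counts as baseline: "Since Day 1 corresponds to the date of first dose, Day 1 will be used for baseline". SAP 6.4.2.1 and Appendix 2 add that Day 1 assessments were to be done before the first dose.

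SAP 6.2 sets the level: "All statistical tests will be conducted at a two-sided 0.20 significance level". SAP 6.2.3 adds: "No adjustments will be made for multiple testing".

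The objectives name post-baseline days only. Protocol 2.1 reads "To evaluate the WHO Clinical Outcome Scale (9-point scale) at Day 3, Day 5, Day 10, and Day 28", and SAP 2.2 lists the same days plus Day 14.

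Protocol 8.4.2.3 planned a different method: "An ordinal logistic regression analysis for the specified time points will be presented as odds ratio, with associated 95% CI and p-value". Under Protocol 8.3, regression models were to be stratified by baseline symptom severity and age, which are also the randomisation factors in Protocol 5.3.

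**The concern.** A between-arm test at a pre-dose visit answers no question. Patients are randomised, treatment is blinded and nothing has been taken, so any difference is chance. A p-value below 0.20 there says nothing about the drug, yet it would sit in the same table as the efficacy tests. It could lead readers to discount or over-read the comparisons that follow.

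The SAP is also inconsistent with its own practice elsewhere. For viral load (6.4.2.1) and total symptom score (6.4.3.4) it tests post-baseline visits only and puts the baseline value in the model. For the WHO scale it tests the baseline value and leaves it out of the later comparisons. The SAP gives no reason for this and specifies no effect estimate or interval for the scale.

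**Working it through.** The documents give no operating figure for the WHO-scale tests, so there is none to reproduce.

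**Inputs from the documents**
- Level 0.20, two-sided, no adjustment (SAP 6.2 and 6.2.3).
- Planned allocation: "52 patients to each of 900 mg, 1800 mg, 3600 mg and placebo" (SAP 2.1).
- Contrasts per visit, reading the individual-dose comparisons as each dose against placebo: 1800 and 3600 mg pooled, and 900, 1800 and 3600 mg singly. That makes four.
- Six tested visits, one of them Baseline: 6 × 4 = 24 tests, of which 4 are at Baseline.

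**Step 1: chance of a nominally significant baseline contrast**
- Expected number under the null: 4 × 0.20 = 0.80.
- If the four contrasts were independent: 1 − 0.80⁴ = 0.59. They are not independent, because they share the placebo arm and two of the doses also form the pool.
- Correlations with equal arms: two single-dose contrasts, 1/2 = 0.50; pooled against one of its own doses, 1.5/√(1.5 × 2) = 0.87; pooled against 900 mg, 1/√(1.5 × 2) = 0.58.
- Simulating four contrasts with this structure and a cut-off of 1.2816 (2,000,000 draws) gives 0.439 for at least one rejection.

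**Step 2: does this hold for a coarse scale with ties?** Tie-corrected Mann-Whitney tests at 52 per arm (40,000 trials per scenario, score distributions assumed) give:

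| Assumed baseline scores | At least one p < 0.20 |
|---|---|
| Two scores, 50% to 90% of patients sharing one | 43% to 45% |
| Three levels | 44% |
| 95% to 98% sharing one score | 49% to 50% |
| All identical | 0% |

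**Step 3: effect of stratified randomisation.** Suppose the severity stratum is perfectly balanced, about 70% of patients have moderate or severe symptoms, and the stratum predicts the WHO score (all assumed):

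| P(score 2) with / without moderate or severe symptoms | At least one p < 0.20 |
|---|---|
| 0.80 / 0.50 | 41% |
| 0.85 / 0.40 | 35% |
| 0.90 / 0.30 | 26% |
| 0.95 / 0.10 | 4% |

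So 44% is the nominal-level figure, and a strongly predictive stratum pulls it down.

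**Step 4: what adjusting for baseline might gain.** Assumptions, none of them in the documents: a latent-normal ordinal outcome, a 0.25 SD shift, 60% of patients at baseline score 2 and the rest at 1, and latent baseline-to-follow-up correlation r. The pooled contrast has 104 against 52 patients. Power at two-sided 0.20:

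| r | Mann-Whitney | van Elteren, stratified by baseline score | Gain |
|---|---|---|---|
| 0.3 | 0.52 | 0.54 | 0.02 |
| 0.5 | 0.53 | 0.56 | 0.03 |
| 0.7 | 0.53 | 0.62 | 0.09 |

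A second simulation (20,000 trials, similar assumptions) gives gains of about 0.01, 0.04 and 0.08. Together the range is about 0.01 to 0.09. With no treatment effect, the unadjusted test rejects about 0.20 of the time, as it should.

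**The case against.** The strongest reply is that little depends on this analysis. It is one of the other secondary endpoints, SAP section 1 moves the emphasis to viral load, and no decision uses the baseline p-value. The SAP says it supersedes the protocol where they differ. Mann-Whitney-Wilcoxon needs no proportional-odds assumption and copes with sparse upper scores. The protocol's model was stratified by severity and age, not by the baseline WHO score, so it does not itself support that adjustment. Leaving out the strata is not peculiar to this endpoint either: the primary log-rank test in SAP 6.4.1 is also unstratified. All of this stands, and it limits the importance of the point. None of it gives a reason to test Baseline.

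Three stronger readings are tempting, and the documents do not support them.
- A reader might infer that a chance baseline imbalance biases the later tests or inflates their error rate. In a randomised trial the unadjusted rank test is valid, and chance imbalance is already within its 0.20.
- A reader might count all 24 WHO-scale tests and attribute the high chance of some rejection to the Baseline visit. That chance mostly reflects multiplicity, which SAP 6.2.3 declares openly. Removing Baseline leaves 20 tests and lowers the chance by only about 0.03.
- A reader might state as fact that usable precision is lost. The documents give no score distribution, effect size or baseline-to-follow-up correlation for this scale, and at r = 0.3 the gain is close to nothing.

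**Conclusion.** The point holds, as a minor one. The four Baseline tests are null by design and serve no stated objective. At the nominal level, about 44% of such trials would show at least one significant baseline contrast. That figure assumes that baseline scores vary and are not largely fixed by the severity stratum. It falls to 26% to 41% under moderate to fairly strong assumed dependence on the stratum, falls further if the dependence is stronger, and is zero if every score is the same.

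The post-baseline tests are valid. Ignoring the baseline score and strata may cost some efficiency, about 0.01 to 0.09 in power under the assumptions shown, and the documents do not allow a firmer figure. The harm is uninformative p-values and possibly some lost precision, not bias.

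**What to change.** In SAP 6.4.3.5, delete Baseline from the list of visits tested. The count and percentage summary in that section and Figure 9 already show the baseline distribution, so nothing descriptive is lost. The planned tests fall from 24 to 20.

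For the post-baseline visits, use a van Elteren test stratified by baseline WHO score. Add a rule that the screening score is used when Day 1 is missing. Protocol Appendix 4 schedules the scale at Screening/Baseline as well as Day 1, but the screening fallback in SAP Appendix 2 covers only symptom score and viral load. Without the rule, patients with no Day 1 score would drop out of the stratified test. State also how sparse baseline categories will be combined.

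As an option, use the protocol's ordinal logistic model with baseline score and the randomisation strata, and report an odds ratio with an 80% CI. This gives an effect size, but upper scores may need collapsing if they are sparse.

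The cost is a short SAP wording change, one missing-baseline rule and minor programming. No new data are needed.

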#### **6.4.3.6 Rate of Hospitalization Through Day 28**

The number and percentage of patients who were hospitalized will be presented. The percentage of patients who were hospitalized will be compared using a binary logistic regression analysis. The model will include only the treatment group. Contrasts under this model will allow for the comparisons across treatment groups. The results will be presented as odds ratios, with associated 80% CIs and p-value. The period will cover from the time of randomization to 28 days after, any hospitalization for which date of hospitalization > date of randomization + 28 would be excluded.

A listing with details on hospitalizations will be incorporated as part of the AE listing (Section 7, Listing 9).

#### **6.4.3.7 Rate of Progression to Oxygen Therapy Through Day 28**

The analysis of this endpoint will be performed on the ITT population. The number and percentage of patients who progress to oxygen therapy and type of oxygen therapy will be presented. The percentage of patients who had progressed to oxygen therapy will be compared using a binary logistic regression analysis. The model will include only the treatment group. Contrasts under this model will allow for the comparisons across treatment groups. The results will be presented as odds ratios, with associated 80% CIs and p-value. The period will cover from the time of randomization to 28 days after, any progression to oxygen therapy for which date of progression > date of randomization + 28 would be excluded.

#### **6.4.3.8 Duration of Hospitalization**

The duration of hospitalization will be from the date of first hospitalization until date of discharge [(Date of hospitalization – date of discharge) in the eCRF Form “Adverse Event”]. The duration of hospitalization will be the total number of days hospitalized in case of more than one hospitalization.

The duration of hospitalization will be analyzed on the ITT population in subjects who were hospitalized. Duration of hospitalization will be summarized by treatment group using descriptive statistics (N, mean, median, standard deviation, Q1, Q3, minimum, and maximum). An ANOVA model will be performed to analyze the difference between treatment groups. The model will include only the treatment group.

Contrasts under this model will allow for the comparisons across treatment groups. The results will be presented as mean treatment difference with associated 80% CI and p-value.

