- Duration of hospitalization [duration will be identified in the eCRF Form “Adverse Event” as the difference between date of discharge and date of admission]
- Mortality rate [death will be identified in the eCRF Form “Adverse Event” if outcome of adverse event is fatal]

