### **6.2.2 Handling of Missing Data**

#### **6.2.2.1 Imputation**

Severity Symptom Score: Missing values on severity symptom score will not be imputed. However, where a patient has died, their symptom score will not be considered missing, but will be imputed with the maximum severity score (3) for each symptom at each time point.

Clinical Outcome Scale: Missing values on clinical outcome scale will not be imputed. However, where a patient has died, their clinical outcome scale will not be considered missing, but will be imputed with maximum clinical outcome scale (7 [maximum severity if alive] or 8 [maximum severity if dead]) at each time point.

Viral load: Prior to the log 10 transformation, non-numeric viral load results reported as below the limit of detection will be replaced by the limit of detection divided by 2. As an example, results reported as “<2228cp/mL SARS-CoV2 detected” will be replaced by 1114 cp/mL. Non-numeric viral load results reported as “No SARS-CoV2 detected” will be replaced by 1 cp/mL. Replacing by 1 (instead of by zero) will be done so that the log 10 of viral load will be defined in all subjects (and equal to zero when no SARS-CoV2 is detected).

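### SAP 6.4.3.8 prints the length-of-stay formula in reverse, and no rule gives an end date for a stay without a discharge

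*SAP*

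**What the plan says.** SAP 6.4.3.8 defines the endpoint twice in one sentence. The prose reads "The duration of hospitalization will be from the date of first hospitalization until date of discharge". The bracket that follows, which points to the adverse event form of the eCRF, reads "Date of hospitalization – date of discharge". For repeated admissions the SAP takes "the total number of days hospitalized in case of more than one hospitalization".

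SAP 4.2 defines the same endpoint, from the same form, as "the difference between date of discharge and date of admission". Protocol 7.1.3 also runs from admission to discharge.

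On the analysis, SAP 6.4.3.8 says that duration "will be analyzed on the ITT population in subjects who were hospitalized", and that "An ANOVA model will be performed to analyze the difference between treatment groups". Treatment group is the only term in the model, and there is no censoring.

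The missing-data rules in SAP 6.2.2 cover symptom score, the WHO scale, viral load and viral clearance. For symptoms they say that "where a patient has died, their symptom score will not be considered missing", and the WHO scale has a similar rule. Length of stay has none there, and none in Protocol 8.8.

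**The concern.** There are two separate problems.

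First, the bracket puts the two dates in the wrong order for a subtraction. It is the line closest to a programming instruction. Coded literally, it would reverse the sign of every mean and every treatment difference while leaving the p-value unchanged.

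Second, a patient still in hospital when follow-up ends, or who dies there, may have no discharge date. The plan then offers no way to compute the duration, and an ANOVA silently omits missing values. The handling of these patients would be chosen after the fact, possibly by software default. The plan anticipates death as a missing-data problem for two other endpoints, so its absence here looks like an oversight.

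**Working it through.** The documents give no numerical target for this endpoint, so there is no figure to reproduce. The stays and admission rates below are assumptions, chosen to show direction and scale.

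**1. Direction of the formula.** Assume admission on the 5th and discharge on the 12th.
- SAP 6.4.3.8 bracket: 5 - 12 = -7 days.
- SAP 4.2 order: 12 - 5 = 7 days, or 8 if both calendar days are counted.

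**2. Effect of the sign if coded as printed.** Assume stays of 4, 6 and 9 days in one arm (mean 19/3 = 6.33) and 5, 8, 12 and 7 days in the other (mean 32/4 = 8.0).
- Correct order: 8.0 - 6.33 = +1.67 days; F = 0.616, p = 0.468.
- Reversed: -8.0 - (-6.33) = -1.67 days; F and p are identical.

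**3. A stay still open at the end of follow-up.** Take discharged stays of 4, 6 and 9 days, plus one patient who has been in hospital for 20 days at Day 28.
- Patient dropped: 19/3 = 6.33 days.
- Stay counted to Day 28: (19 + 20)/4 = 9.75 days.

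Dropping the open stay shortens the mean by about 3.4 days.

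**4. A stay ended by death.** The result depends on when the patient died.
- The same three stays plus a death after 6 days: (19 + 6)/4 = 6.25, against 6.33 if dropped. Almost no change.
- Four 4-day stays plus a death after 10 days: (16 + 10)/5 = 5.2, against 16/4 = 4.0 if dropped. Dropping shortens the mean.
- Four 4-day stays plus a death after 2 days: (16 + 2)/5 = 3.6, against 4.0 if dropped. Dropping lengthens the mean.

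The sign of the bias is therefore not fixed for deaths.

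**5. How much data is involved.** With 52 patients per arm and an assumed admission rate of 3% to 10%, an arm has 52 × 0.03 = 1.6 to 52 × 0.10 = 5.2 admissions, or about 2 to 5. One lost stay is then 1/5 to 1/2 of the arm's data, 20% to 50%.

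**6. Whether another passage supplies an end date.** None does.
- SAP 6.4.3.6 limits the admission date to 28 days after randomization. It does not say when a stay stops being counted.
- Protocol 4.4.5 follows vital status to Day 28 ± 2, but ongoing serious events for up to 28 days (± 2) after the last dose.
- Protocol Appendix 1 ends adverse event reporting 30 days after the last dose.

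These limits differ, and none is tied to length of stay.

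**The case against.** The strongest reply on the formula is that the plan's intention is clear. The prose of the same sentence, SAP 4.2 and Protocol 7.1.3 all run from admission to discharge. The bracket might only name the start and end fields, with the dash marking a span. A table of negative stays would be noticed at first output. Most of this stands. A reader might infer that the plan produces negative stays and would report a benefit as a harm; read as a whole, it does not support that. The span reading is weaker, because SAP 6.4.1 and 6.5.1 use the same dash for subtraction, with the later date first. The bracket remains wrong as printed.

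On the missing end date, the reply is that the SAP excludes nobody for lacking a discharge date. A patient drops out only if the field is blank, and the eCRF instructions are not in the documents; a site may enter the death date there. Protocol 7.2.1 also provides for days of hospitalization and death to be collected from hospital records. This stands as a limit on the point: the gap is an unstated derivation rule, and actual loss of patients is not shown.

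Finally, deaths would not be hidden. SAP 6.4.3.9 analyses them separately, the WHO scale scores them at its maximum, and Listing 10 reports them. That also stands.

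**Conclusion.** The bracket in SAP 6.4.3.8 is wrong as written and should be aligned with SAP 4.2. It is probably a slip. Separately, the plan has no rule for a stay that is open at the end of follow-up or ended by death. If the discharge field is blank, that patient leaves the ANOVA. For open stays, this can shorten the arm's mean, on the assumption that they are longer than average.

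A reader might go further and infer that the worst stays drop out, so that the error favours the worse arm. The documents do not support this. Loss of fatal stays depends on eCRF entry that is not shown, fatal stays need not be long, and the examples above move the mean either way.

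The impact is small. This is one of the other secondary endpoints, it is analysed only in hospitalized patients from an outpatient trial, and SAP section 1 puts the emphasis for the proof-of-concept decision on viral load. The 20% to 50% figure rests wholly on the assumed admission rate.

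**What to change.** In SAP 6.4.3.8, replace the bracket with discharge date minus admission date, summed over admissions, and use the same wording in SAP 4.2. Then add three rules:
- **Open stays.** Count a stay still open at Day 28 or last contact up to that date, and flag it in the table. Say which date defines Day 28, since SAP 6.4.3.6 counts from randomization and Appendix 2 from first dose.
- **In-hospital deaths.** State the end date used, flag these stays, and show the summary with and without them. Ending a stay at death can make an early death look like a short stay, and a flag alone does not change the ANOVA estimate.
- **Day counting.** Use the plain difference unless an inclusive count is chosen deliberately. The added day in SAP 3.2 and 6.5.1 concerns days on treatment and need not carry over.

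The cost is a few lines of SAP text and one extra summary. The SAP already uses admission, discharge, death and study completion dates, so no new data collection appears to be needed. The change should be made before unblinding.

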#### ***8.4.2.6. Duration of Hospitalization***

The duration of hospitalization will be performed on the ITT population. Duration of hospitalization will be summarized by treatment group using descriptive statistics (N, mean, median, standard deviation, standard error, CI, minimum, and maximum). Linear regression will be performed to analyze the difference between treatment groups. The results will be presented as mean treatment difference with associated 95% CI and p-value.

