## 1 INTRODUCTION

The purpose of this statistical analysis plan (SAP) is to present the statistical methodology that will be used for the final analysis of DalCor Pharmaceuticals DAL-401. This plan also provides a description of the tables, figures and listings that will be included in the final statistical report. It is based on the protocol dated 22-OCT-2020 and on the annotated case report form (CRF) version 1.0. In case of differences in terms of descriptions or explanations between the SAP and the clinical protocol, the SAP will supersede the protocol. Any deviation to this SAP would be reported in the statistical report.

Since the protocol was developed and discussed with the regulatory authorities, a greater understanding of COVID-19 and clinical trials in COVID-19 has emerged. New variants have also been observed and their clinical course needs to be taken into consideration. Based on this emerging knowledge, a higher emphasis will be placed on viral load analyses when interpreting the data and deciding on POC in this study. Less emphasis will therefore be placed on the current primary endpoint of Patient Reported Outcomes and endpoints that look at changes in symptoms of COVID-19. Certain symptoms such as loss of taste and loss of smell as well as cough are chronic symptoms which may not resolve over the course of a 28-day study. In view of this the endpoints evaluating symptoms will not include taste, smell or cough in some analyses.

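### Duration of hospitalization is tested only among patients who were admitted, so the comparison is not a randomized one and can be biased in either direction

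*SAP*

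**What the plan says.** SAP 6.4.3.8 sets the analysis set: "The duration of hospitalization will be analyzed on the ITT population in subjects who were hospitalized". The method follows: "An ANOVA model will be performed to analyze the difference between treatment groups", with treatment group as the only term. The output is inferential: "The results will be presented as mean treatment difference with associated 80% CI and p-value".

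Protocol 8.4.2.6 says: "The duration of hospitalization will be performed on the ITT population". It plans a linear regression with a mean difference, 95% CI and p-value. Protocol 7.1.3 measures duration from first admission to discharge. Where the two documents differ, the SAP governs: "In case of differences in terms of descriptions or explanations between the SAP and the clinical protocol, the SAP will supersede the protocol".

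Admission is itself tested for a treatment effect in SAP 6.4.3.6: "The percentage of patients who were hospitalized will be compared using a binary logistic regression analysis". For all tests, SAP 6.2 says "All statistical tests will be conducted at a two-sided 0.20 significance level" and SAP 6.2.3 says "No adjustments will be made for multiple testing". The sensitivity analyses in SAP 6.4.4 concern the primary endpoint only.

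**The concern.** Randomization makes the arms comparable as randomized. It does not make comparable the subsets who later go into hospital, if treatment affects who goes. A drug that keeps the milder cases at home leaves only the longer stays in its arm and appears to prolong hospitalization. A drug that adds short admissions appears to shorten it. Neither result describes what the drug did to time spent in hospital.

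The plan attaches a p-value at the two-sided 0.20 level to this contrast, so a misleading difference could be reported as a treatment signal, favourable or unfavourable.

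**Working it through.** **Inputs.** There are 52 patients per arm (SAP 2.1), so 104 in the two highest doses combined against 52 on placebo, tested at two-sided 0.20 (SAP 6.2). The plan gives no admission rate, stay length, standard deviation or power for this endpoint, so there is no figure of its own to reproduce. All rates and stay lengths below are assumptions.

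**Step 1: mean among the admitted.** Let half of placebo admissions last 3 days and half 10. The drug prevents a fraction f of the short stays and leaves the long ones unchanged.

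Mean among the admitted = [3(1 − f) + 10] / (2 − f)

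- f = 0 (placebo): 13 / 2 = 6.5 days
- f = 0.5: 11.5 / 1.5 = 7.67 days (+1.17)
- f = 1: 10 / 1 = 10 days (+3.5)

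The admission rate cancels, so in this scenario the direction does not depend on it. The size depends on the mix. If three quarters of placebo stays are short, the placebo mean is 0.75 × 3 + 0.25 × 10 = 4.75. The drug mean is then (1.125 + 2.5) / 0.625 = 5.8 (+1.05) for f = 0.5 and 10 (+5.25) for f = 1.

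**Step 2: mean over all randomized patients, 0 if never admitted.** With placebo admission rate r and the half-and-half mix, the mean is (r/2) × [3(1 − f) + 10].

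| r | Placebo | f = 0.5 | f = 1 |
|---|---|---|---|
| 2% | 0.13 | 0.115 (−0.015) | 0.10 (−0.03) |
| 5% | 0.325 | 0.2875 (−0.0375) | 0.25 (−0.075) |
| 10% | 0.65 | 0.575 (−0.075) | 0.50 (−0.15) |

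Hospital days fall in every row, while the SAP's contrast rises.

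**Step 3: the opposite direction.** Let the drug double the short stays (f = −1). The mean among the admitted is (6 + 10) / 3 = 5.33, which is 1.17 days better than placebo. Over all randomized patients at r = 10% it is 0.05 × 16 = 0.80 against 0.65, which is 0.15 days worse.

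**Step 4: how often a misleading result would appear.** Simulation of 104 against 52 patients, 20,000 trials per scenario, half-and-half mix, no deaths. Stays vary around 3 and 10 days with a standard deviation of one third of the mean, rounded to whole days with a minimum of 1. The test is a two-group ANOVA, a simplification of the SAP's model, which also contains the other arm. Ranges run from f = 0.5 to f = 1. The first two result columns count only trials in which the test could be computed.

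| r | Drug looks longer | Longer with p < 0.20 | Test not computable | Same wrong-direction result, all randomized |
|---|---|---|---|---|
| 5% | 63% to 83% | 16% to 37% | 10% to 18% | 3% to 6% |
| 10% | 68% to 91% | 20% to 52% | 0.5% to 1% | 4% to 6% |

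The nominal rate in one direction is 10%. With no drug effect the hospitalized-only test gave 8% at r = 5% and 9.5% at r = 10%, so the excess comes from the selection.

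**Step 5: how many stays there would be.** Expected admissions in an arm of 52 are 52r, and the chance of none is (1 − r)^52.

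- r = 2%: 1.04 expected; 35% chance of none
- r = 5%: 2.6 expected; 7% chance of none
- r = 10%: 5.2 expected; 0.4% chance of none

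At the lower rates, some single-dose contrasts may rest on one or two stays or not be estimable.

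**The case against.** Length of stay has a natural meaning only for people who were admitted, and prevented admissions are examined elsewhere without this restriction: the admission rate (SAP 6.4.3.6), mortality (6.4.3.9) and the WHO scale at each visit (6.4.3.5), which has separate levels for hospitalized states and death. A reader with all the tables would see fewer admissions beside the longer mean stay. This stands as a limit on the risk of misreading. It does not repair the duration contrast, its interval or its p-value.

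A reader might also infer that the SAP narrowed an analysis that the protocol ran on everyone. The documents do not support that. Protocol 8.4.2.6 names the ITT population, but the definition in Protocol 7.1.3 has no value for a patient never admitted, and neither document assigns such patients zero days. The protocol leaves the matter open, and it had already planned a p-value.

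Finally, an all-patient comparison with deaths ranked worst partly repeats the rate and mortality analyses. That is true, and it is a cost of the fix.

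**Conclusion.** The concern holds: the planned test compares subsets selected after randomization, and no other analysis in the SAP corrects it. Its size is unknown, because it depends on admission rates, stay lengths and which admissions the drug affects. Under the half-and-half assumption the distortion is +1.17 to +3.5 days against a drug that in fact reduces hospital days. The upper figure requires every short stay and no long stay to be prevented, so it is an extreme and not an expected value.

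Three stronger readings are tempting and not supported:

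- That the bias always runs against the drug. Step 3 shows the reverse.
- That early death is counted as benefit. SAP 4.2 and 6.4.3.8 use the discharge date and say nothing about a patient who dies in hospital. The gap is an unspecified rule, unlike the symptom score and WHO scale, for which SAP 6.2.2.1 sets a value at death.
- That durations will come out negative. The bracketed formula in SAP 6.4.3.8 does subtract in the wrong order, but SAP 4.2 and the sentence containing the bracket both run from admission to discharge. It is a slip to correct.

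The endpoint sits in the other-secondary tier, and the primary analysis and sample size do not depend on it. Priority is low to moderate.

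**What to change.** In SAP 6.4.3.8:

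1. Make the between-arm comparison on all ITT patients. Use days alive and out of hospital from randomization to Day 28, in which days after death count as zero, so deaths have a defined value and a mean difference with its interval can be reported. The alternative is hospital days to Day 28, with 0 for patients never admitted, compared by a rank test with deaths ranked worst. A worst rank supplies no number of days, so that version should carry no mean difference.
2. Keep duration among hospitalized patients as a descriptive summary by arm, without a p-value, and say how in-hospital deaths enter it.
3. Correct the bracketed formula to discharge minus admission, as in SAP 4.2.

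The cost is SAP wording and a short derivation, with no new assessments. Because it changes what is compared, it should be recorded as a change to the endpoint analysis before unblinding. One check is needed first. SAP 4.2 takes admissions and their dates from the adverse event form, while Protocol 7.2.1 keeps non-fatal serious events of worsening COVID-19 out of the safety database yet asks for days in hospital to be collected. The SAP should name a source that captures COVID-19 admissions.

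The downsides are many zeros or ties, an estimate that is small in days (0.015 to 0.15 in the Step 2 table), and partial overlap with the admission-rate and mortality analyses.
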